#### Exploratory outcomes:

We will also evaluate the impact of the Hypertension Plus system on medication use in terms of number and dose of antihypertensive medication and other cardiovascular preventative treatment (statins, antiplatelets, anticoagulants). We will examine subgroups as listed below. We will investigate intervention fidelity in terms of adherence to the monitoring schedules.

#### Timeframe of outcome measurement

"Time 0" for exposed patients will be the date on which they start using the Hypertension Plus monitoring system. For unexposed patients "Time 0" will be the median date on which exposed patients in the same general practice started using the Hypertension Plus system. Longitudinal data for all TM101-A

Protocol Template for a Research Study\_version 15.0CONFIDENTIAL© Copyright: The University of Oxford and Oxford University Hospitals NHS Foundation Trust 2019Page 17 of28

outcomes (BP measurements, consultation dates etc.) will be extracted from patient's electronic health record from the 12 months before and after "Time 0" for all patients.

#### Covariates

Covariates will be any factors that may confound the relationship between use of the Hypertension Plus system and the primary outcome which have been identified from our previous research. These are:

- Age (years)
- Gender
- Ethnicity (White, Black, Asian, Mixed, Other)
- Smoking status (current, ex or non)
- Index of Multiple Deprivation
- Body mass index (kg/m^2)
- Total cholesterol (mmol/L)
- Systolic and diastolic blood pressure (clinic or home readings)
- Past medical history:
  - Diagnosis of diabetes (Type 1 or 2)
  - Previous myocardial infarction or stroke
  - Diagnosis of chronic kidney disease
  - Estimated glomerular filtration rate (eGFR, ml/min/1.73 m^2)
- Medication use:
  - Statin treatment (drug type and dose)
  - o Antihypertensive medication use (drug type and dose, defined daily dose)
  - o Other current cardiovascular medication
- Electronic Frailty Index and/or characteristics making up the electronic frailty index
- Health Economic Resource use including consultation rate, timing, personnel undertaking, referrals and admissions.

Covariates will be defined using the closest available electronic healthcare records data prior to "Time 0" for all patients, but within the previous two years. Otherwise this data will be regarded as missing.

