# 12.2. Procedure for Accounting for Missing, Unused, and Spurious Data.

Due to the use of random effects models, missing data is only expected in covariate data. The primary analysis will use multiple imputation by chained equations to impute missing values, including the outcome(s) in the imputation model. Initially 5 imputed datasets will be created and estimates will be combined across imputations using Rubin's rules. Further imputations will be added if the Monte-Carlo error of estimates exceeds 10% of the corresponding standard error. Multiple imputation will only be employed if variables are missing in less than 20% of patients. For larger proportions of missing data, the covariate will be removed from analyses. Sensitivity analyses will be conducted using complete data only.

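### One two-year look-back covers every covariate, so ethnicity and diagnoses coded earlier are lost or misread although they are in the record

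*Protocol*

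**What the plan says.** Section 11.2, Covariates, names the factors thought to confound the link between system use and the primary outcome. The list mixes two kinds of item. Some are measured repeatedly: BMI, cholesterol, BP, eGFR, medication and resource use. Others are fixed or are lifetime histories: ethnicity, diabetes, "Previous myocardial infarction or stroke" and "Diagnosis of chronic kidney disease". One closing rule governs the whole list. The value is the closest record before Time 0, "but within the previous two years. Otherwise this data will be regarded as missing". No item is exempt, and the text does not say how the absence of a diagnosis code is to be read.

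Section 12.2 then fixes what happens to missing covariates: "The primary analysis will use multiple imputation by chained equations to impute missing values". It adds a limit: "Multiple imputation will only be employed if variables are missing in less than 20% of patients". Beyond it: "For larger proportions of missing data, the covariate will be removed from analyses".

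Three other places bear on this. Under Statistical modelling, covariates enter as fixed effects without selection, and the effects at 6 and 12 months come from comparing modelled BP between exposed and unexposed patients. The Subgroup analysis list includes previous MI or stroke, and ethnicity. Section 8.1 asks practices only for the previous two years of data.

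**The concern.** A two-year window makes sense where an old value is stale. A stroke coded five years ago is not stale: the patient has had a stroke. The rule nevertheless calls that record missing, and an ethnicity code entered once at an earlier date meets the same fate. The information is in the clinical system and the plan's definition discards it.

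The 20% rule can compound the loss. A variable emptied by the look-back may be removed from the model altogether, although the protocol names it as a confounder and says that bias from variables affecting allocation must still be dealt with. Patients here choose whether to use the system, so the between-group comparisons rely on that adjustment. Baseline tables would also describe the two groups wrongly.

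**Working it through.** The protocol states no missingness rate or code-age distribution, so there is no figure of its own to reproduce. All rates below are assumptions, shown as ranges.

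**1. Ethnicity, coded once.** Let time since coding be exponential with mean T years. The share older than two years is exp(−2/T).

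| T (years) | Share set to missing | Under section 12.2 |
|---|---|---|
| 1 | 13.5% | imputed |
| 2 | 36.8% | removed |
| 5 | 67.0% | removed |
| 10 | 81.9% | removed |
| 15 | 87.5% | removed |

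The 20% limit is reached when exp(−2/T) = 0.20, that is T = 2/ln 5 = 1.24 years. Re-coding within two years would lower these shares.

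**2. Diagnoses, coded once.** Let prevalence be p, with code dates spread evenly over the past D years. The share of true cases inside the window is 2/D. For D = 5 to 20 that is 40% down to 10%. The protocol does not define a negative, so there are three possible readings, each taken with p = 5% to 30%:

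- **A. No code in the window means missing.** Missing share = 1 − p × 2/D. Lowest: 1 − 0.30 × 0.40 = 88%. Highest: 1 − 0.05 × 0.10 = 99.5%. The covariate is removed.
- **B. Only cases with an older code are missing.** Missing share = p × (1 − 2/D). Lowest: 0.05 × 0.60 = 3%. Highest: 0.30 × 0.90 = 27%. Below 20% they are imputed although every one is a known positive; at 20% or more the covariate is removed.
- **C. No code in the window means absent.** Nothing is missing, but only 10% to 40% of true cases are recognised.

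The readings are alternatives, and each one yields a wrong covariate.

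**3. Effect on the estimates.** Assume a time-fixed confounder with effect −6 mm Hg, prevalence 10% in exposed and 20% in unexposed patients, and a true intervention effect of −3 mm Hg. The patient SD of 17, measurement SD of 10, 25% uptake and the −3 are the protocol's own sample-size assumptions; the confounder's effect and prevalences are not.

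- *Dropped, no baseline BP.* Shift = −6 × (0.10 − 0.20) = +0.60, so the post-Time 0 level contrast is −2.40.
- *Misclassified (reading C, D = 10, 20% of cases recognised), no baseline BP.* Hidden cases among patients without a code in the window: exposed 0.08/0.98 = 8.2%, unexposed 0.16/0.96 = 16.7%. Shift ≈ 6 × 0.085 = +0.51, so about −2.49.
- *Dropped, with baseline BP.* One reading has reliability 17²/(17² + 10²) = 289/389 = 0.743, and the mean of two 289/339 = 0.853. Remaining shift: 0.60 × 0.257 = 0.15, or 0.60 × 0.147 = 0.09.

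A simulation of 300 datasets of 4,000 patients without baseline BP agrees: −2.98 with the confounder kept, −2.38 dropped, −2.48 misclassified (Monte Carlo SE 0.04).

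**4. The difference-in-differences term.** A time-fixed covariate with a constant effect adds the same amount before and after Time 0, so it cancels. In the same simulation the pre/post term was −3.00 in all three cases.

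**The case against.** The strongest reply is that the design already protects the main effect. The protocol uses difference-in-differences, and fixed main effects such as ethnicity or past diagnoses leave that interaction where it is. This stands. A reader might infer that the central effect estimate is badly biased; step 4 does not support that. It does not remove the concern, because the plan also reports 6- and 12-month comparisons of modelled BP levels, and those do depend on adjustment.

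Second, systolic and diastolic BP are themselves listed covariates. Adjusting for baseline BP absorbs most of the assumed bias, from about 0.6 to about 0.1 mm Hg. This also stands.

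Third, it is tempting to say that all these values are missing because of their true value, so that imputation must fail. That holds only for diagnoses under reading B, a hybrid which the text does not state. For ethnicity, missingness would follow the coding date, and at high missingness the item is removed, not wrongly imputed.

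Fourth, a reader might infer that the MI/stroke and ethnicity subgroups lose most of their members. The subgroup list sets no window, and the two-year sentence speaks only of covariates. The loss follows only if the subgroups borrow the covariate definitions.

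Finally, sections 11.1 and 12.4 allow for a later SAP that could settle look-back by item. They make it conditional, however, and the protocol has already stated a rule.

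**Conclusion.** The point holds as a defect of definition. The protocol applies a single two-year window to items that do not expire, exempts none of them, and couples this to removal of any covariate missing in 20% or more of patients. No reading of an absent diagnosis code gives a correct covariate.

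Its size cannot be fixed from the document, which says nothing about how often practices re-code these items. If ethnicity is coded once, it falls under the removal rule unless the mean time since coding is below about 1.24 years. For diagnoses, the assumed ranges leave 60% to 90% of true cases outside the window. The resulting shift in the 6- and 12-month level contrasts is modest, about 0.1 to 0.6 mm Hg against an assumed effect of 3 mm Hg. It rests on one assumed confounder effect and prevalence gap, and is at the low end once baseline BP is in the model. Baseline tables are affected as well, and the two subgroups if they share the definitions. This should be corrected; it does not threaten the difference-in-differences interaction.

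**What to change.** In section 11.2, Covariates, split the look-back by type of item:

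- Keep the two-year window for repeatedly measured items: BMI, cholesterol, eGFR, smoking, BP, medication and resource use.
- For ethnicity, diabetes, previous MI or stroke and chronic kidney disease, use any record before Time 0. State that a diagnosis never coded counts as absent.
- State that the MI/stroke and ethnicity subgroups use these same definitions.
- Confirm that the electronic search returns codes older than two years, since section 8.1 requires only two years of practice data and section 9.6 gives no look-back for past medical history.

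With this change the two-year rule makes none of the fixed or lifetime items missing; only ethnicity never coded would remain so, at a rate the protocol does not give. The 20% removal rule need not change for this purpose; whether to impute above 20% is a separate choice. The cost is a few lines of text and one search setting, best settled before data are extracted.

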## Summary statistics and figures

Continuous covariate data and mean BP before "Time 0" will be summarised by the mean and standard deviations or median and inter-quartile range for non-normally distributed data. Normality will be determined through visual inspection of histograms and Q-Q plots. Binary/ categorical data will be summarised by mean and proportions. Summary statistics will be presented in tables overall and by exposure category.

Scatterplots of BP values over time will be produced, with exposed and unexposed groups denoted by different symbols.

## Statistical modelling

Multilevel models and Difference-in-Differences (DiD) analysis will be used to describe changes in outcomes over time (12 months before and after "Time 0") and the effect of the introduction of the Hypertension Plus system. Difference-in-differences (DiD) allows comparison of differences in outcomes, TM101-A

Protocol Template for a Research Study\_version 15.0 CONFIDENTIAL
© Copyright: The University of Oxford and Oxford University Hospitals NHS Foundation Trust 2019 Page 18 of
28

before and after an intervention, between groups. Bias from unobserved fixed variables within each group is automatically accounted for in this type of analysis but bias from variables that affect allocation to the exposed an unexposed group must still be accounted for.

• Primary outcome (SBP) and secondary DBP outcome:

For the primary outcome (SBP) and secondary outcome of DBP, multilevel linear models will be used to model these outcomes over time, including a fixed linear effect for time relative to "Time 0" and random effects for patient and practice level average BP. The models will also include as fixed effects, an indicator for whether each BP was measured in the clinic or at home, an indicator for exposure and, to estimate difference-in-differences, interaction terms between the exposure and time period variable (initial model).

The addition of random effects for patient and practice level trends into the initial model will be considered by comparing models via the likelihood ratio test and Akaike Information Criterion (AIC), with terms retained if model fit is significant improved or the AIC is lower. Covariates will be included as fixed effects without selection once the initial model is finalised. To account for autocorrelation between BP measurements in the same individual, standard errors will be estimated using robust methods and more specifically the Huber-White Sandwich estimator of the variance which can adjust for within-cluster correlation.

The effect of the Hypertension Plus intervention at 6 and 12 months will be estimated by comparing the estimated BP values in the exposed at unexposed groups at these time points, as derived from the models. These estimates, and estimates from the models will be summarised in tables including p-values and 95% confidence intervals.

Model assumptions will be checked by producing histograms of residuals and scatter plots of residuals against fitted values. If there is evidence of violation of assumptions, models will be refitted to log-transformations of SBP and DBP and assumptions re-checked.

• Secondary BP control outcome:

For the secondary outcome of BP control, a multilevel logistic regression model will be fitted to the BP control data, using the same steps as described above for the BP outcomes above.

• Primary care workload:

The number of primary care consultations occurring before and after "Time 0" will be totalled separately and modelled using a negative binomial model, including an offset term for person-time of follow-up (to account for potential loss-to-follow-up). This model will include an indicator for time before/ after "Time 0", an indicator for the exposure variable, and an interaction between these variables. Random effects for the patient and practice will also be included and robust standard errors will be estimated similar to other models.

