## 9.5. Description of study intervention and comparator

## 9.5.1. Description of study intervention

The study intervention is "Hypertension Plus". People using the system will use an app to send blood pressure readings securely to a central dashboard. Data will be recorded automatically in the clinical record via appropriate SNOMED codes allowing identification of active users. An active user will be someone with a record of having used the Hypertension Plus system in their clinical record with the appropriate SNOMED code. This definition will be regardless of how much use is made of the system and once labelled as having received the intervention, patients will be analysed in that group on an "intention to treat basis".

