## 11.2. Description of the Statistical Methods

#### **Exposures**

The primary exposure will be use of the Hypertension Plus monitoring system, defined by SNOMED codes recorded in the clinical system compared to no use. The date on which the patients started using the system ("Time 0") will be extracted and patients will be classified as exposed from this date onwards. These patients will be classified as unexposed prior to this date. Where a practice or individual stops using the system, this will be classed as the end of exposure. Patients who never use the system will form the unexposed group.

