## Subgroup analysis

Analyses and modelling above will be repeated in the following subgroups:

• Men and women

TM101-A

Protocol Template for a Research Study\_version 15.0CONFIDENTIAL© Copyright: The University of Oxford and Oxford University Hospitals NHS Foundation Trust 2019Page 19 of28

- Age >65 years; >80 years
- Mean SBP before "Time 0" (>160 mm Hg)
- Previous history of myocardial infarction or stroke
- By CCG area
- Users of the system for at least 6months defined as coded data identifying use recorded in the clinical record at both baseline and between months 6-12
- People with baseline blood pressure ≤140/90 compared to those >140/90mmHg
- Deprivation score (High vs Low)
- Ethnicity

Sample size requirements for this study were determined through simulation, as there is little statistical literature for sample size requirements for multilevel modelling. Data was simulated for systolic BP measurements, nested within patients, nested within practices, with the same structure as that detailed in the statistical modelling section. Normal distributions for BP values and variances around patient and practice mean values were assumed (reflecting random intercept terms). A global mean BP of 148 mm Hg was assumed, with practice variation (standard deviation, SD) of 5 mm Hg about this mean. Within a practice, patient variation (SD) was assumed as 17 mm Hg and measurements within a patient were assumed to vary by 10 mm Hg (SD) about the patient mean. The effect of time was assumed to be 0, clinic BP measurements were assumed to be 5 mm Hg higher than home measurements and 25% of patients were expected to take up the Hypertension Plus system.

Assuming an effect size of -3 mm Hg (BP 3 mm Hg lower in patients using the Hypertension Plus system) and a minimum of 4 BP measurements for each patient, 1000 simulated datasets were created and multilevel models as described in the statistical modelling section were fitted to each simulation. This demonstrated that to achieve 90% power at the 5% significance level for the effect of the Hypertension Plus system, 100 patients each drawn from 8 general practices would be required for this study (800 patients in total, 91% power).

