# 12.3. Potential biases

# (Adapted from Parker et al In Press 2021)

Bias	Issues		Mitigat	tion

(1) Confounding due to non- randomised

	a)	Patients will not be randomised and there is likely to be variation in implementation between practices.	a)	Analysis will take into account area as similar
design	b) c)	Non-participating patients (comparator group) may be systematically different at baseline from those in the telemonitoring group. Practices who take part may be different to those who do not	b) c)	implementation by area Use practices prior to implementation as comparators Within areas
			This is a study s possibi confou taken i	consider ordering effects an observational o there is always the lity of some residual nding that can not be nto account.
(2) Information bias	BP mea differe leading	asured in the clinic and at home may be nt due to white coat and masked effects g to confounding in terms of change in BP .	a)	In a linear mixed model this can be fully adjusted by adding the

The following table summarises key biases and the mitigation we propose.

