# TM101-A

Protocol Template for a Research Study\_version 15.0

© Copyright: The University of Oxford and Oxford University Hospitals NHS Foundation Trust 2019 Page 21 of 28

		intervention/control in the analysis b) BP control rather than BP level in analyses
(3) High variability in the frequency of readings	Home readings can be several times per day or week whereas clinic readings tending to be 1-4x per year. Furthermore, attendance at clinic may be for some other reason meaning those who attend or not are different systematically	
 
a) Primary analysis utilises all available data
 
b) Consider sensitivity analysis using standardisation of readings over time. This means that we take bp values at fixed time points more specifically at 6 and 12 months with value closest to that time point being the one used for the analysis.
 

(4) Contamination of readings	Home readings can be coded as clinic readings. The automated importing of Hypertension Plus readings into the clinical record should avoid this but it is possible that home readings in the comparator group may also be contaminated as may be readings prior to the implementation period.	
 
a) This may be a problem in both groups
 
b) Hypertension Plus readings will be labelled as such
 

(5) Regression to the mean	People chosen on the basis of raised baseline readings are more likely to have subsequently controlled BP	Both intervention and comparison groups will be chosen using same attributes Consideration of need for matching.
(6) Measurement error	Both operator, system and monitor errors are possible	Operator errors may be more likely by patients but evidence of operator bias is more likely for clinicians. Most of these errors will be similar in both groups
(7) End digit preference	People tend to be more likely to record readings ending in zero	
 
a. We will investigate prevalence in both intervention and comparator groups
 
b. Adjusting for the control/intervention group in a mixed model should be
 

		able to take into account for potential differences in the magnitude of digit preference
(8) Withdrawal bias	Patients may not use the Hypertension Plus system consistently.	We will use intention to treat approach so individuals with any Hypertension Plus activity recorded will be assigned to intervention.

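### The primary BP model uses one clinic/home offset for everyone, so the system effect is unbiased only if users and non-users have the same mean clinic-home gap, a condition the protocol neither states nor tests

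*Protocol*

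**What the plan says.** Protocol 11.2 (Statistical modelling) gives SBP and DBP a multilevel linear model with linear time, random patient and practice intercepts, an exposure indicator and "an indicator for whether each BP was measured in the clinic or at home". The difference-in-differences comes from "interaction terms between the exposure and time period variable (initial model"). No term lets the clinic-home gap differ between users and non-users. The only optional extensions are random trends.

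On timing, 11.2 (Exposures) sets Time 0 at first use of the system, and "patients will be classified as exposed from this date onwards". Section 9.5.1 says "People using the system will use an app to send blood pressure readings securely to a central dashboard". The bias table in 12.3 adds that home readings may come several times a day or week, against one to four clinic readings a year.

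The same table recognises that clinic and home BP differ through white-coat and masked effects. Its mitigation begins "In a linear mixed model this can be fully adjusted by adding the" and, after a page turn, continues "intervention/control in the analysis". Its second mitigation is to analyse BP control. For uneven reading frequency it offers a possible sensitivity analysis using the value nearest 6 and 12 months.

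In the sample-size simulation, "clinic BP measurements were assumed to be 5 mm Hg higher than home measurements", with no separate value for users.

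**The concern.** For users, the start of exposure and the move towards home readings happen together. Non-users have no matching change at their assigned Time 0. A shared offset subtracts the same amount from every home reading. If users' own gap is larger than that amount, the remainder appears as a fall in BP after Time 0 in users only, and the interaction reports it as a system effect. If users' gap is smaller, a real effect is partly hidden.

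The protocol makes unequal gaps possible without showing that they exist:

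- White-coat and masked effects act in opposite directions and vary between patients.
- Users choose the system, and 12.3 accepts that they may differ from comparators at baseline.
- Section 11.2 keeps the lowest reading of each day, which lowers values more where several are taken per day.

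The listed mitigations do not relax the condition. BP control uses 140/90 for clinic and 135/85 for home in both groups, which is again one fixed 5 mm Hg shift. The nearest-value analysis takes whatever reading type is closest. The simulation states a single gap, so it could not show the sensitivity.

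**Working it through.** **Inputs from the protocol (11.2, 12.1).** 25% users; at least 4 readings per patient; base SDs 5 (practice), 17 (patient) and 10 (reading); conservative SDs 10, 22 and 14; effects of -3 and -1 mm Hg; 800 patients for the base case and 12,600 for the combined conservative case; 5% significance.

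**Assumptions, not in the protocol.** Two readings before and two after Time 0; two-sided test; period taken as before/after; 15% home readings in non-users and in users before Time 0; 80% or 95% home in users afterwards. Practice variance is left out because it largely cancels in a within-practice difference-in-differences. Results are from generalised least squares with a normal approximation.

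**The plan's own figure.** Ignoring reading type, the SD of a patient's change is 10 × √(1/2 + 1/2) = 10. SE = 10 × √(1/600 + 1/200) = 0.816. Power for -3 mm Hg = Φ(3/0.816 - 1.96) = 95.7%. With the clinic/home indicator and the assumed shares, the SE is 0.893 to 0.942 and power is 92% to 89%. The stated 91% lies between these. It can be matched but not confirmed, because the protocol gives no home shares.

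**How a gap difference enters.** Let g_U and g_N be the mean gaps, Δh the rise in users' home share (non-users: none), and w the users' weight in the common gap estimate. Users' measured change is -g_U Δh. The model adds back Δh × [w g_U + (1 - w) g_N]. What remains is

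bias = -Δh × (1 - w) × (g_U - g_N).

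- 15% to 80% home: 0.47 per 1 mm Hg (Δh = 0.65, so 1 - w = 0.73).
- 15% to 95% home: 0.65 per 1 mm Hg (Δh = 0.80, so 1 - w = 0.81).
- Complete switch (0% to 100%): users carry no information on their own gap, w = 0, and the leakage is 1.0.
- No change in home share, or equal gaps: no bias.

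**False-positive rate with no true effect**, Φ(|bias|/SE - 1.96) + Φ(-|bias|/SE - 1.96):

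| Patients | SDs (patient/reading) | Users' home share after | SE | Gap difference 1 mm Hg | Gap difference 2 mm Hg |
|---|---|---|---|---|---|
| 12,600 | 17/10 | 80% | 0.225 | 56% | 99% |
| 12,600 | 17/10 | 95% | 0.237 | 78-79% | 100% |
| 12,600 | 22/14 | 80% | 0.315 | 32-33% | 85-86% |
| 12,600 | 22/14 | 95% | 0.332 | 50% | 98% |
| 800 | 17/10 | 80% | 0.893 | 8% | 18% |
| 800 | 17/10 | 95% | 0.942 | 11% | 28% |

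For example, in row 1: 0.472/0.225 = 2.10 and Φ(0.14) = 56%. Where two values are shown, they differ by whether reading types are averaged exactly or drawn at random.

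**With an exposure-by-reading-type term**, the bias is 0.00 in all these cases. If users have no home readings before and no clinic readings after Time 0, the term cannot be estimated.

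**Lowest-of-day rule.** For two independent same-day readings with SD 10, the expected minimum lies 10 × 0.564 = 5.6 mm Hg below the mean. This is an upper illustration, since same-day readings are correlated.

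**The case against.** The protocol names the clinic/home problem, models reading type, labels system readings and admits residual confounding. Nothing in it says that the gap differs by group, and every gap difference above is assumed. Extra interactions and sensitivity analyses are often left to a SAP. The first two points stand, and they limit this to a conditional bias. The SAP point carries less weight: section 11.1 makes a SAP optional, while 11.2 already fixes the primary model.

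A reader might go further in three ways that the document does not support.

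- **That the protocol claims the clinic/home indicator adjusts fully.** The table cell breaks at a page turn, and as it reads the thing added is the intervention/control term. Words may be missing. Neither a group main effect nor a common reading-type offset would remove this bias, but the sentence cannot be pinned to the indicator.
- **That reading type and exposure are almost the same variable.** Clinic readings can continue after Time 0, and 12.3 expects some home readings in comparators and before implementation. Leakage is then partial.
- **That a 1 mm Hg difference usually makes an ineffective system significant at the planned size.** The 12,600 figure comes from the larger SDs, under which the rate is about 33-50%.

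**Conclusion.** The concern holds as a condition that is neither stated nor tested. The primary estimate is unbiased only if users and non-users have the same mean clinic-home gap. If they do not, about 0.5-0.7 mm Hg per 1 mm Hg of gap difference enters the estimate under the assumed shares, and up to 1.0 under a complete switch. At 12,600 patients with no true effect, a 1 mm Hg difference is declared significant about 56-79% of the time (SDs 17/10) or 33-50% (SDs 22/14), and a 2 mm Hg difference about 86-100%. At 800 patients with the base SDs, the 1 mm Hg rate is about 8-11% against a nominal 5%. The document does not show that the gaps differ, so this is not evidence that the result will be biased.

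**What to change.** Keep the planned model as primary. Prespecify two analyses to be reported beside it:

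- (a) the same SBP and DBP model with an exposure-by-clinic/home interaction, provided users have both reading types;
- (b) a difference-in-differences restricted to clinic readings before and after Time 0 in both groups.

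In row 2 of the 12.3 bias table, state that the adjustment requires an equal clinic-home gap in users and non-users.

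No new data are needed, because 11.2 already identifies readings as clinic or home. The cost is precision. At 12,600 patients the SE rises from about 0.23-0.33 to 0.27-0.49 with the interaction and to about 0.4-1.0 for clinic readings only. With SDs 22/14, power for -1 mm Hg falls from about 85-89% to 55-76% in analysis (a); the primary analysis keeps its own power. Analysis (a) fails under a complete switch and does not correct a lowest-of-day effect that arises only after Time 0. Analysis (b) depends on who still attends clinic after Time 0, which 12.3 warns may be selective. Neither repairs home readings coded as clinic.
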